4.1.1 Length of the Study

The total duration of the study for each patient will be up to 112 weeks divided as follows:

- Screening Period: up to 28 days (4 weeks)
- Treatment Period: Day 1 Cycle 1 continues with repeating treatment cycles of 28 days until patients discontinue study treatment or at end of study (EOS; defined as 2 years [104 weeks] post initial dose).
- Safety follow-up: until 28 days (4 weeks) after the last dose of study treatment or until initiation of another anti-cancer therapy, whichever occurs first (see Section 1.2 for safety assessments at follow up).

Patients will be asked to return to the clinic 28 days (± 7 -day window) after the last dose of study medication to complete Final Visit assessments. In the event that the decision to withdraw from the study occurs after 28 days from the last dose of idasanutlin, e.g., due to interruption of intended cycle continuation due to an AE, then the Final Visit should occur on or as close as possible to the date of withdrawal. The visit at which a response assessment shows *no response* (NR) or PD may be used as the Final Visit if treatment is discontinued.

4.1.2 Dose-Escalation Decision Criteria

Intra-patient dose-escalation from 150 mg to 200 mg may be allowed *at Cycle 4 or 5* for patients who have demonstrated adequate tolerability *but have a lack of Hct control or inadequately controlled leukocytosis and/or thrombocytosis at the end of Cycle 3*. The goal is to bring these patients to a *better* hematologic response by end of Cycle 5 to allow for assessment for durability of response through Week 32. PK samples will be taken from these dose-escalated patients at the beginning of Cycle 4 to assess PK characteristics at the higher dose compared to Cycle 1.

Patients with progressive disease will not be permitted to dose-escalate and the patient should come off the study.

Consideration for dose-escalation will be based on a review of patient data, including but not limited to, response assessments, laboratory, and safety data. All intra-patient dose-escalation decisions will be made in consultation with the Investigator and Sponsor, including the Medical Monitor and Safety Science Leader.

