- 10 Complete blood count (see Appendix 9 for details). Differential counts may be manual or automated, but must occur with each hematology assessment, with emphasis on determination of the presence of peripheral blasts.
- 11 See Appendix 9 for details.
- 12 Serum pregnancy testing is required for females of childbearing potential during the Screening Period (within 7 days of Cycle 1 Day 1). Cycle 2 and beyond, urine or serum pregnancy test should occur prior to every cycle. If a urine pregnancy test is positive, it must be confirmed by a blood pregnancy test. Pregnancy test (urine or serum) can be done anytime during the study if clinically indicated.
- 13 PK samples collected Cycle 4 only if dose escalation to 200 mg takes place in a patient with no response/no Hct control after first 3 cycles following discussion with Sponsor.
- 14 Final Visit (± 7 days): Patients who discontinue will be asked to return to the clinic for a final visit within 28 days after the last dose. In some instances, the visit at which a response assessment shows progressive disease may be used as the final visit. Alternatively, final visit may be the EOS, defined as 2 years post initial dose.
- 15 For JAK2V617, JAK2 exon 12 and p53 mutational analysis (DNA). See Appendix 2.

Table 1 Overall Schedule of Activities (cont.)

- 16 Routine MRI (or CT) within 7 days of screening does not need to be repeated if it meets the study specifications (i.e., Day –35 to –1). Splenic imaging required at Cycle 5 Day 28 only if reduction in spleen volume is <35% at Cycle 3 Day 28. Composite response captured only if splenic imaging is completed Cycle 5 Day 28. Patients without protocol-defined splenomegaly at baseline (i.e. spleen <450 cm³ on MRI or CT at baseline) *do not need to undergo further spleen imaging.*
- 17 On Day 28 of every 3 cycles after Week 32 up to two years after first dose (i.e., timing if no dose delays occur Cycle 11 Day 28, Cycle 14 Day 28, Cycle 17 Day 28, Cycle 20 Day 28, Cycle 23 Day 28, etc.). Note, bone marrow histology and cytogenetics Day 28 every 6 cycles post Week 32 (i.e., timing if no dose delays occur Cycle 14 Day 28, Cycle 20 Day 28, etc.) *for* up to 2 years per PI discretion in context of complete hematologic response.
- 18 Cytogenetics preferentially on bone marrow aspirate sample. Blood sample will be utilized if bone marrow result is inconclusive.

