Cycle 4	Day 1	0 PreDose		x	x								
		1		x									
		2		x									
		4		x									
		6		x									
	10 ^e		x										
	Day 2	PreDose		x	x								
	Day 5	0 PreDose		x	x								
		1		x									
		2		x									
		4		x	x								
6			x	x									
10 ^e		x	x										
Cycle 5	Day 28 ^g	N/A				x				x			
End of Cycle 8 (32 weeks) and Beyond ^{h, g}		N/A				x				x			
No Response or Disease Progression ⁱ		N/A				x				x			

N/A= not applicable; NR=no response; PD=Disease Progression; PDy=pharmacodynamic; PK=pharmacokinetic; RBR=Research Biosample Repository; TBNK=T, B, and NK.

^a Cycle 4 PK and MIC-1 only for patients with incomplete response and dose escalation to 200 mg after Cycle 3.

^b For JAK2 V617 and JAK2 exon 12 mutational analysis (DNA) all timepoints, p53 mutational analysis (DNA) only Cycle 1 Day 1 0 predose and at NR/PD.

Table 2 Detailed Schedule of Activities (cont.)

- ^c In cases of Dose Delay where Week 32 occurs prior to the End of Cycle 8 any assessments performed at Week 32 would not need to be repeated at the End of Cycle 8.
- ^d Samples for RBR DNA will be collected on Day 1 from all patients who signed RBR Informed Consent. If, however, the RBR DNA blood sample is not collected during the scheduled visit, it may be collected at any time during the conduct of the clinical study.
- ^e (-)2 hour window for 10-hour timepoints.
- ^f For Cycle 3 and beyond, ECGs must be performed on Days 1 and 2 (24-hour timepoint, prior to the dose when applicable) and 4, 6, and 24 hours post dose only if there is evidence of QTc prolongation > 30 ms during Cycle 1 and Cycle 2 once the patient has received study medication as compared with the QTcF interval of the screening ECG. Otherwise, ECGs will NOT be required for Cycle 3 and beyond unless the investigator considers it necessary on behalf of the patient's safety. An unscheduled ECG can be performed at any time as clinically indicated. See Section 8.2.3 (Electrocardiograms) for ECG requirement for Cycle 3 and beyond.
- ^g (-)3/(+)1 day window for C3D28, C5D28 and end of Cycle 8 (Week 32). Must be prior to start of subsequent cycle.
- ^h On Day 28 of every 3 cycles after Week 32 up to two years after first dose (i.e., Cycle 11 Day 28, Cycle 14 Day 28, Cycle 17 Day 28, Cycle 20 Day 28, Cycle 23 Day 28, etc.), including the end of study visit.
- ⁱ No response by ELN 2009 or Progressive Disease ([Appendix 1](#)).

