It is important to note that the bone marrow of PV patients is more similar to solid tumor than AML patients; therefore the lower solid tumor MTD (250 mg SDP eq) daily × 5 days is considered more relevant as reference for PV patients. The desirable outcome for PV would be to utilize a tolerated dose (lower than the solid tumor MTD) needed for p53 induction as demonstrated by MIC-1 (i.e., 150 mg) utilizing the 5-day schedule with the goal of preferentially targeting MDM2-addicted CD34+ PV cells and while at the same time sparing patients the cytopenic side-effects associated with higher exposures. Idasanutlin monotherapy doses at a level equal to 150 mg daily × 5 days is projected to be associated with a tolerable safety profile and appears suitable for prolonged treatment of PV patients.

In an Investigator-led, open-label Phase I study of single agent oral idasanutlin in patients with PV and ET, idasanutlin has been tested at 100 mg and 150 mg SDP daily × 5 days. Thus far, these lower doses, which are lower than the MTD identified in solid tumor or AML patients, have shown clinical efficacy and are tolerated in the PV patient population.

In this Phase II study, intra-patient dose-escalation from 150 mg to 200 mg may be considered *at Cycle 4* for patients who have a lack of Hct control *or who have inadequately controlled leukocytosis and/or thrombocytosis* at end of Cycle 3. Note that due to the MTD at 250 mg, intra-patient dose escalation will be limited to 200 mg to balance the potential for improving a patient response with higher exposure with the potential for increased side effects. The goal is to optimize the response by the end of Cycle 5 in order to assess 12-week response duration by Week 32. PK and MIC-1 samples will be taken at the beginning of Cycle 4 from these dose-escalated patients to confirm increased exposure and p53 pathway induction with dose increase as compared to Cycle 1 (Section 4.1.2).

Further details are provided in the [Idasanutlin IB](#).

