6.6 DOSAGE MODIFICATION

Intra-patient dose-escalation from 150 mg to 200 mg is allowed after Cycle 3 (*preferable at Cycle 4, or latest, Cycle 5*) for patients who have demonstrated adequate tolerability and are showing a lack of Hct control *and/or inadequately controlled leukocytosis and/or thrombocytosis* at end of Cycle 3 (Section 4.1.2). Patients with PD will not be permitted to dose-escalate and should come off the study. Consideration for dose-increase will be based on a review of patient data, including but not limited to, safety data, response assessments and laboratory data. All intra-patient dose-escalation decisions will be

made in consultation with the Investigator and Sponsor, including the Medical Monitor and Safety Science Leader.

In case of hematologic toxicity (i.e., anemia, thrombocytopenia and/or neutropenia), patients may need treatment interruptions and/or dose reductions (see Table 8).

Guidance for dose-reductions for AEs is described in Section 8.3.9. Furthermore, after one year of treatment (end of Cycle 13), a reduction of the idasanutlin dose to 100 mg for all subsequent cycles may occur for any patient that has not previously had a reduction to 100 mg for other reasons to generate data for longer term tolerability. This reduction will be based on communication between the Investigator and Sponsor. Treatment may be re-escalated back to the prior highest tolerated dose if Hct increases to $\geq 45\%$ and/or CHR response is lost ($WBC \geq 10 \times 10^9/L$ and PLT count $> 450 \times 10^9/L$) to achieve a hematologic response. Treatment *must* not be re-escalated if the patient has progressive disease (see Appendix 1).

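### PK and MIC-1 sampling at 200 mg is scheduled in Cycle 4 only, so a patient first escalated at Cycle 5 has no scheduled 200 mg sample

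*Protocol*

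**What the plan says.** **When escalation may happen.** Protocol Section 4.1.2 permits the step from 150 mg to 200 mg at Cycle 4 or 5. Section 6.6 gives the timing as "preferable at Cycle 4, or latest, Cycle 5". Section 4.3 refers to Cycle 4 only. All three sections admit two kinds of reason at the end of Cycle 3: lack of hematocrit control, or inadequately controlled leukocytosis and/or thrombocytosis.

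**When the higher dose is sampled.** Every statement names Cycle 4:
- Section 4.1.2 (PK, with Cycle 1 as the comparator): "PK samples will be taken from these dose-escalated patients at the beginning of Cycle 4 to assess PK characteristics at the higher dose compared to" […].
- Section 4.3 (PK and MIC-1): "PK and MIC-1 samples will be taken at the beginning of Cycle 4 from these dose-escalated patients to confirm increased exposure".
- Table 1 footnote 13 (PK): "PK samples collected Cycle 4 only if dose escalation to 200 mg takes place in a patient with no response/no Hct control".
- Table 2 footnote a (PK and MIC-1): "Cycle 4 PK and MIC-1 only for patients with incomplete response and dose escalation to 200 mg after Cycle 3".

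**What the samples are for.** Section 4.3 gives the aim: "to confirm increased exposure and p53 pathway induction with dose increase as compared to Cycle 1". PK parameters are a secondary endpoint; serum MIC-1 is exploratory (Table 3).

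**The concern.** The sampling cycle and the permitted escalation cycles do not match. A site that follows the schedule for a patient whose first 200 mg dose falls in Cycle 5 finds no PK or MIC-1 time point at that dose. The block cannot easily be improvised. Section 6.1 (Table 4) requires dosing in the clinic on PK days, while Table 1 footnote 6 lets Days 2 to 5 be taken at home, so a profile over Days 1, 2 and 5 has to be arranged in advance. The profile of a patient's first cycle at 200 mg cannot be collected afterwards.

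The stated reasons for sampling also differ. Footnote 13 speaks of patients with no response or no hematocrit control. A patient whose hematocrit is controlled but who is escalated for white cells or platelets falls outside that wording, even when escalated at Cycle 4.

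What is at stake is the evidence that the dose step does what Section 4.3 expects of it, in what is likely to be a small group of escalated patients.

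**Working it through.** The plan gives no figure to reproduce. The check is a count from Table 2 and a comparison of texts.

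1. **Cycle 4 block, PK.** Day 1 at 0, 1, 2, 4, 6 and 10 h = 6; Day 2 pre-dose = 1; Day 5 at 0, 1, 2, 4, 6 and 10 h = 6. Total 6 + 1 + 6 = 13.
2. **Cycle 4 block, MIC-1.** Day 1 pre-dose = 1; Day 2 pre-dose = 1; Day 5 pre-dose, 4, 6 and 10 h = 4. Total 1 + 1 + 4 = 6.
3. **Cycle 1 block.** The same time points appear for PK (13) and MIC-1 (6). The design is therefore a time-matched comparison within patient, 200 mg against 150 mg.
4. **Cycle 5 and later.** The only Cycle 5 row is Day 28, with nucleic acid whole blood and cytokine plasma. The later rows carry the same two sample types. PK = 0 and MIC-1 = 0.
5. **Scheduled samples at 200 mg, by first 200 mg cycle:**

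| First 200 mg cycle | PK | MIC-1 |
|---|---|---|
| Cycle 4 | 13 | 6 |
| Cycle 5 | 0 | 0 |

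6. **Size of the contrast sought.** Section 2.2.2 reports approximate dose-proportionality over 100 to 2400 mg/day and inter-patient variability of about 40% to 50%. Under proportionality the expected exposure ratio is 200/150 = 1.33. A step of that size is easier to see within a patient than between patients, so profiles from Cycle 4 escalators do not directly replace the missing pair.
7. **Who is to be sampled.** Sections 4.1.2 and 4.3 say escalated patients, having just listed both kinds of reason. Table 2 footnote a says incomplete response plus escalation, which can be read to include patients escalated for counts. Only Table 1 footnote 13 is confined to no response or no hematocrit control. For a patient with controlled hematocrit escalated for counts, footnote 13 points one way and the other three texts the other.

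**The case against.** The strongest case on the other side is that the gap is small and can be worked around. Section 6.6 prefers Cycle 4, so perhaps no patient escalates at Cycle 5. Section 8.5 allows unscheduled PK samples to characterise the PK profile better, and the sponsor takes part in every escalation decision and could ask for them. Section 9.4.4 plans population PK as well as non-compartmental analysis, so data from other patients and doses still contribute. All analyses are descriptive, no decision rule uses these samples, and the SAP (Sections 5.7.3 and 5.10) plans no exploratory or biomarker analysis for the abbreviated report.

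Much of this stands and limits the point. It does not close the gap: Section 8.5 is optional, covers PK only and does not mention escalation, and assessments at unscheduled visits under Section 8.9.5 are likewise made only as deemed necessary.

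Three stronger readings are tempting and are not supported:
- **That Cycle 5 escalators can have no 200 mg data at all.** Section 8.5 permits unscheduled PK, so the accurate statement is that none is scheduled.
- **That they would be sampled in Cycle 4 at 150 mg and counted as 200 mg, pulling the apparent increase towards none.** Both footnotes make sampling conditional on escalation, and Sections 4.1.2 and 4.3 refer to patients already escalated. Section 9.4.4 tabulates concentrations by dose level. The expected result is missing data, not mislabelled data.
- **That patients escalated for counts are left out of sampling throughout.** The restriction sits in footnote 13 alone, and Table 1 itself refers to the detailed schedule for time points.

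**Conclusion.** The inconsistency is real and should be corrected. For any patient first escalated at Cycle 5, scheduled sampling at 200 mg falls from 13 PK and 6 MIC-1 samples to none, and the purpose given in Section 4.3 cannot be met from scheduled samples. The count rests on Table 2 as printed and on Sections 4.1.2 and 6.6 meaning what they say about Cycle 5. If Section 4.3 alone governed, and escalation were confined to Cycle 4, this part of the problem would disappear; the documents do not settle that.

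The documents do not give the number of such patients. The effect is on a secondary PK objective and an exploratory marker, not on the primary endpoint. The conflict over footnote 13 is separate and narrower: it concerns one footnote, but it can affect patients escalated at Cycle 4 as well.

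**What to change.** In Sections 4.1.2 and 4.3, Table 1 footnote 13 and Table 2 (the Cycle 4 block and footnote a), replace the fixed cycle with the first cycle at 200 mg. Name both PK and MIC-1, and apply the rule to every patient escalated for any reason the protocol permits. That wording also removes the restriction in footnote 13, and it is neutral on timing.

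Separately, reconcile Section 4.3 with Sections 4.1.2 and 6.6 on the cycles in which escalation may occur. Which of them is right is a clinical matter on which this point takes no view, and the sampling change should not write an escalation cycle into Section 4.3.

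The cost is a wording amendment. A Cycle 5 escalator would have the same 13 PK and 6 MIC-1 samples one cycle later. A patient escalated for counts would have the block that Sections 4.1.2 and 4.3 already describe. No change to the PK analysis is needed, since Section 9.4.4 already works by dose level.

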4.2 SCIENTIFIC RATIONALE FOR STUDY DESIGN

The study rationale is provided in Section 2.1.

4.2.1 Rationale for Study Population

It has previously been shown that in primary hematopoietic cells from PV patients with JAK2V617F mutation that reduced expression of p53 occurs as a result of increased LA autoantigen expression leading to increased translation of MDM2 (Nakatake et al. 2012). It would appear that JAK2V617F induces this ribonucleoprotein and furthermore, LA protein expression can be down-regulated by in vitro JAK2 inhibitor treatment. Lu et al. demonstrated increased MDM2 expression and reduced p53 levels in PV patients' JAK2V617F-positive CD34+ cells (Lu et al. 2012). Nutlin-3, a small molecule antagonist of MDM2, was shown to inhibit the proliferation of PV CD34+ cells through increased p53-mediated apoptosis (Lu et al. 2012, Lu et al. 2014). Thus, the use of idasanutlin would be anticipated to enhance p53 activity by different mechanisms and presents a novel approach to the treatment of PV.

Patients with PV who require cytoreductive therapy because of risk features or increasing phlebotomy needs have poorer survival. As previously noted, PV patients can experience symptoms such as fatigue, pruritus, thrombotic complications (stroke, myocardial infarction, etc.) and some patients will have transformation of their disease to MF, MDS or AML.

Resistance or intolerance to HU, as defined by the modified ELN criteria (Barosi et al. 2010) was found to occur in 11% and 13% of patients with PV, respectively. Resistance to HU was associated with higher risk of death (hazard ratio [HR] 5.6; 95% confidence interval [CI] 2.7%–11.9%; $p < 0.001$) and transformation (HR 6.8; 95% CI 3.0%–15.4%; $p < 0.001$).

As described in Section 2.2.1, patients with PV who are resistant or intolerant to HU have few therapeutic options and there is a need for improved second-line treatments for this patient population.

Therefore, the HU-resistant or intolerant population is an appropriate population for the clinical testing of MDM2 antagonists.

Patients who are resistant or intolerant to second-line ruxolitinib treatment have limited treatment options and represent a high unmet medical need. About one-third of patients discontinued ruxolitinib treatment over 5 years in the ruxolitinib RESPONSE trial (Kiladjian et al. 2018). In this situation, there is no standard of care available for

these patients to maintain Hct control and/or hematologic remission, which exposes this subgroup to risk of PV complications such as thrombosis. Based on the known mechanism of action of idasanutlin, patients who are resistant or intolerant to ruxolitinib may derive clinical benefit from idasanutlin treatment.

4.2.2 Rationale for Biomarker Assessments

MIC-1 (macrophage inhibitory cytokine 1) is a secretory protein that is strongly upregulated by activated p53, and can be detected in the blood of patients treated with idasanutlin as demonstrated in the solid tumor study, NP27872, and the AML study, NP28679 (see [Idasanutlin IB](#)). MIC-1 levels can be determined by a sensitive ELISA test and serve as a serum biomarker for p53 activation, the intended mechanism of action.

Blood samples will be tested for the molecular status of JAK2. Nucleic acid-based monitoring of JAK2 mutation status will be performed as a means of examining changes in disease burden by mutational allele monitoring. Monitoring of JAK2 mutational allelic burden is an important component to measure pharmacodynamic response in PV patients. The expected prevalence of TP53 mutation is low in PV patients (2%–3%) and will be tested at baseline. Additional assessment of TP53 mutation status may be performed at progression to investigate whether extended administration of idasanutlin drives an emergence of TP53 mutation.

MDM2 protein expression in myeloid cells will be assessed as an exploratory biomarker predictive of response. Understanding whether elevated MDM2 protein is a predictive biomarker of idasanutlin activity may also have diagnostic utility.

Understanding the effects of idasanutlin on PV patient immune cell context will be assessed by TBNK panel testing. Towards this understanding, absolute counts and percentages of mature T, B, and NK lymphocyte populations as well as CD4+ and CD8+ T-cell subset ratios in human peripheral blood in response to treatment will be assessed.

4.2.3 Rationale for Clinical Outcome Assessments

Patients with PV often experience a variety of symptoms, most commonly including, but not limited to fatigue and itching (Stein et al. 2014), which can contribute to considerable burden on their health-related quality of life (HRQoL) (Abelsson et al. 2013), and ultimately impact functioning and daily living (Scherber et al. 2010). Since PV patients experience considerable burden, collecting information on the patient experience during treatment is important to be able to comprehensively quantify treatment benefit.

In order to better understand treatment characteristics and effects, information from the patient perspective on disease and treatment-related symptoms, functioning, and HRQoL will be collected through the inclusion of clinical outcome assessment (COA) measures, allowing a better understanding of the patient experience. In this study, the

following COAs will be administered: MPN-SAF TSS, EORTC QLQ-C30, and PGIC. Additional details about these COAs are provided in Section 8.1.2.

4.3 DOSE JUSTIFICATION

During Phase 1 development, two formulations were tested: microprecipitated bulk powder (MBP) and spray-dried powder (SDP); the relative bioavailability of SDP to MBP is approximately 2. For clarity, the doses of MBP tested have been re-designated to SDP equivalent (SDP eq) in this section.

Serum levels of macrophage inhibitory cytokine (MIC-1), a secreted protein that is strongly induced by activated p53, have been used to assess pharmacodynamic effects of idasanutlin in Phase 1 studies NP27872 and NP28679 (see [Idasanutlin IB](#)). Analysis of patients on 50 to 400 mg (SDP eq) daily × 5 days idasanutlin showed that the minimum level for p53 induction occurs at a dose of 50 mg (SDP eq)/day or a corresponding plasma level of 500 ng/mL of idasanutlin. In comparison, a weekly dosing schedule had a less pronounced effect on MIC-1.

A comparison of MIC-1 elevation between the idasanutlin dosing schedules demonstrated limited ability to activate p53 with the weekly schedule. The daily × 3 days dose regimen did not achieve steady-state exposure, displayed shorter duration for SD (median 57 and 103 days for daily × 3-day and daily × 5-day schedules, respectively), and did not alleviate thrombocytopenia. Therefore, the daily × 5-day schedule was chosen as optimal for future clinical trials.

In a study of idasanutlin-treated patients with solid tumors, NP27872, the 5-day schedule MTD was determined to be 250 mg (SDP eq) QD, in a 28-day cycle. Thrombocytopenia, neutropenia, febrile neutropenia and diarrhea were dose-limiting toxicities (DLTs). PK and safety data showed that there was an apparent pharmacokinetic/pharmacodynamic relationship between an AUC per cycle and Cycle 1 platelet nadir. In the AML study, NP28679, a protocol-defined MTD, with or without concomitant 1 g/m² cytarabine, was not achieved. Instead, 300 mg (SDP eq) BID for 5 days in a 28-day cycle was determined to be the maximum tolerable threshold based on GI tolerability.

It is important to note that the bone marrow of PV patients is more similar to solid tumor than AML patients; therefore the lower solid tumor MTD (250 mg SDP eq) daily × 5 days is considered more relevant as reference for PV patients. The desirable outcome for PV would be to utilize a tolerated dose (lower than the solid tumor MTD) needed for p53 induction as demonstrated by MIC-1 (i.e., 150 mg) utilizing the 5-day schedule with the goal of preferentially targeting MDM2-addicted CD34+ PV cells and while at the same time sparing patients the cytopenic side-effects associated with higher exposures. Idasanutlin monotherapy doses at a level equal to 150 mg daily × 5 days is projected to be associated with a tolerable safety profile and appears suitable for prolonged treatment of PV patients.

In an Investigator-led, open-label Phase I study of single agent oral idasanutlin in patients with PV and ET, idasanutlin has been tested at 100 mg and 150 mg SDP daily × 5 days. Thus far, these lower doses, which are lower than the MTD identified in solid tumor or AML patients, have shown clinical efficacy and are tolerated in the PV patient population.

In this Phase II study, intra-patient dose-escalation from 150 mg to 200 mg may be considered *at Cycle 4* for patients who have a lack of Hct control *or who have inadequately controlled leukocytosis and/or thrombocytosis* at end of Cycle 3. Note that due to the MTD at 250 mg, intra-patient dose escalation will be limited to 200 mg to balance the potential for improving a patient response with higher exposure with the potential for increased side effects. The goal is to optimize the response by the end of Cycle 5 in order to assess 12-week response duration by Week 32. PK and MIC-1 samples will be taken at the beginning of Cycle 4 from these dose-escalated patients to confirm increased exposure and p53 pathway induction with dose increase as compared to Cycle 1 (Section 4.1.2).

Further details are provided in the [Idasanutlin IB](#).

